#### 16.3.1 Calculation Exploratory Endpoints

Assuming little or no extra-hepatic clearance of OZ439 and under the assumptions of the well-stirred model, the following exploratory endpoints will be calculated [Yang et al, 2007]:

- Extraction ratio (ER) =  $CL_{iv}/(Q_h \cdot BPratio)$ , where
  - $CL_{iv}$  is the average IV plasma clearance (ml/min) estimated in Part 1 of the study
  - $Q_h$  is an estimation of the liver blood flow:  $Q_h = 1450 [Davis \& Morris, 1993] * (\text{mean BW}/70\text{kg})^{0.75}$  ml/min; mean BW is the mean bodyweight of the subjects in Part 1.
  - BPratio is the Blood:Plasma ratio=1.2 as reported in the CIB [CIB v3.0 2011]
- Liver First Pass (Fh) =  $1-ER$
- Fraction absorbed (Fa =  $F_{tot}/F_h$ ), where
  - $F_{tot}$  is the average total bio-availability estimated in Part 1 of the study

The deconvolution of absorption profile over time for OZ439 will be performed using appropriate software.

## 16.3.2 Statistical Analysis

### Part 1:

To determine the absolute bioavailability, an analysis of variance (ANOVA) will be performed on OZ439 PK parameter  $AUC_{0-\infty}$  using the SAS procedure for mixed effect models (PROC MIXED). The PK parameter will be natural logarithm transformed prior to analysis. The model will include a fixed effect for treatment (i.e. OZ439 oral or OZ439 iv), and a random effect for subject.

From the ANOVA model the back-transformed least-squares means (LSMeans) for test (OZ439 oral) and reference (OZ439 iv) treatments will be presented. The ratio of the LSMean for the comparison of oral and iv OZ439 (i.e. the absolute bioavailability) will be obtained by exponentiating the difference of the LSMean on the log scale. The absolute bioavailability and the corresponding 90% CI will be presented.

The individual bioavailability values will also be reported for each subject.

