## 6.0 Study Design

### Part 1

This is an open-label study in 8 healthy subjects to determine the absolute bioavailability of OZ439 following a single oral dose of OZ439 and a simultaneous single iv infusion of [ $^{14}C$ ]-OZ439 radiolabeled microdose administered at the anticipated  $t_{max}$  of the oral dose. Subjects will receive the following treatment:

Treatment A: a single oral dose of 800 mg OZ439 simple granules administered as a 100-mL dispersion followed by a 15-minute 10-mL iv infusion of 100  $\mu g$  [ $^{14}C$ ]-OZ439 (47 kBq [1.27  $\mu Ci$ ]) beginning 3 hours after the oral dose administration.

### Part 2

This is an open-label, randomized, single-dose, 3-way cross-over study in 18 healthy subjects. Each subject will participate in 3 treatment periods and each subject will receive a single dose of each of the following 3 treatments in a randomized order with a 14-day wash-out period between each treatment:

Treatment B: a single oral dose of 800 mg OZ439 simple granules administered as a 64.5-mL dispersion

Treatment C: a single oral dose of 400 mg OZ439 simple granules administered as a 64.5-mL dispersion

Treatment D: a single oral dose of 400 mg OZ439 simple granules administered as a 64.5-mL dispersion and co-administered with a 150 mg cobicistat tablet (CYP3A4 inhibitor)

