### 10.3 Pharmacokinetic

The PK set will consist of all subjects who receive at least 1 dose of OZ439 and provided sufficient bioanalytical assessment results to calculate reliable estimates of at least one of the primary endpoints PK parameters or secondary endpoint parameters. This set will be used for descriptive statistics of PK parameters.

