### 10.4 Pharmacokinetic Summary

The PK summary set will consist of all subjects who are considered evaluable for the primary statistical analysis, defined as follows:

For Part 2, a subject will be considered evaluable for the primary statistical analysis if they have sufficient PK data to estimate the primary endpoints  $C_{max}$  and  $AUC_{0-inf}$  for the 3 treatments.

For Part 1, a subject will be considered evaluable for the primary statistical analysis (bioavailability) if they have sufficient PK data to estimate the primary endpoint  $F_{po}$ .

This set will be used for the statistical analysis of the treatment comparisons defined in Section 16.3.1.

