	calculated by linear regression of the terminal log-linear portion of the concentration vs. time curve. Linear regression of at least three is required (regression of two points will be flagged).	If adjusted Rsq $\leq$ .80 then parameter is flagged		cobicistat
t 1/2	Terminal phase half-life expressed in time units.	HL_Lambda_z from WNL If adjusted Rsq $\leq$ .80 then parameter is flagged	iv and oral	OZ439 and cobicistat
CL/F	Apparent oral clearance, calculated	Cl_F_obs from WNL	oral	cobicistat
CL	Clearance, calculated as dose/AUC 0-inf	Cl_obs from WNL	iv	OZ439
V d	Volume of distribution at terminal phase, calculated as CL/ $\lambda_z$	Vz_F_obs from WNL	iv	OZ439
F po	Absolute bioavailability, calculated as: $F = (AUC_{\text{oral}} * D_{\text{iv}}) / (AUC_{\text{iv}} * D_{\text{oral}})$ , where AUC oral is the AUC 0-inf of OZ439 and AUC iv is the AUC 0-inf of [  C]-OZ439; D oral is the oral dose and D iv is the iv microdose			OZ439

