### 16.3 Pharmacokinetic Parameters

PK parameters for total radioactivity, OZ439 and cobicistat will be estimated using non-compartmental methods with Phoenix WinNonlin® Version 6.3.

The plasma PK parameters will be estimated from the concentration-time profiles for all subjects in the safety population. In estimating the PK parameters, BQL values at the beginning of the profile will be set to zero. BQL values that occur after the first quantifiable point will be considered missing. Values that are embedded between BQLs, or quantifiable values occurring after 2 or more BQLs, will be set to missing at the discretion of the pharmacokineticist.

Actual blood sampling times will be used in the PK parameter calculations. If the actual time or dose time is missing, the scheduled time may be substituted in order to calculate the PK parameter.

The terminal elimination rate constant ( $\lambda_z$ ) will be determined by plotting the concentration data versus time on a semi-logarithmic scale. The time interval of the terminal elimination phase will be determined by visual inspection. Linear regression on log-transformed concentrations within this interval will be used to calculate the terminal elimination rate constant. At least 3 data points are required to obtain a reliable  $\lambda_z$  and associated parameters. Points prior to and including  $C_{max}$  will not be used to estimate  $\lambda_z$ . Terminal half-life and  $\lambda_z$  values (and derived parameters) will be flagged if  $\lambda_z$  cannot be accurately estimated (adjusted  $r^2 < 0.8$ ). In calculations of AUC parameters, the linear up / log down trapezoidal method will be used. For  $AUC_{0-inf}$ , if the %extrapolation from last quantifiable concentration to infinity  $>20\%$ , then the data will be flagged.

Descriptive statistics (number of subjects, mean, geometric mean, SD, CV%, median, minimum, and maximum) will be used to summarize the calculated PK parameters by treatment. For  $t_{max}$ , the geometric mean will not be presented.

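### The Part 1 ANOVA omits dose, so the ratio it calls absolute bioavailability is 8000 × F at the nominal doses (AUCs in common units)

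*SAP*

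**What the plan says.** Section 6.0 gives the Part 1 treatment as "a single oral dose of 800 mg OZ439 simple granules administered as a 100-mL dispersion followed by a 15-minute 10-mL iv infusion of 100"; the last figure is in µg and refers to [14C]-OZ439. Each subject therefore supplies an oral and an iv AUC.

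Section 16.1 defines Fpo as (AUC_oral × D_iv)/(AUC_iv × D_oral), using AUC0-inf of OZ439 and of [14C]-OZ439. It explains that D_oral "is the oral dose and D iv is the iv microdose". The same section gives AUCs in units of concentration × time, so they are not per unit dose.

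Section 16.3.2, Part 1, applies PROC MIXED to AUC0-inf. The one transformation it names is the logarithm: "The PK parameter will be natural logarithm transformed prior to analysis". The model has a fixed effect for treatment and a random effect for subject. The section then says: "The ratio of the LSMean for the comparison of oral and iv OZ439 (i.e. the absolute bioavailability) will be obtained by exponentiating the difference"; the difference meant is between log-scale LSMeans. It asks for this value with its 90% CI, and for the individual bioavailability values as well.

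The SAP states dose normalisation in only two places: for Treatment C in the Part 2 comparison of B with C, marked as applying to that comparison alone (16.3.2), and for Treatment C in one concentration plot (16.2).

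**The concern.** Two sections give two rules for one primary endpoint, and the rules do not agree. A programmer who follows 16.3.2 literally has no reason to divide by dose in Part 1, because the SAP says so explicitly where it wants dose normalisation.

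Fpo is the sole Part 1 primary endpoint (5.1.1). A dose-corrected geometric mean of Fpo may also appear among the descriptive statistics, which "will be used to summarize the calculated PK parameters by treatment" (16.3). The 90% CI, however, comes only from this model. It goes into Tables 4 and 15.2.3, and Table 15.2.3 is also sent to the sponsor at the interim (7.2). Run as written, the estimate and both limits would be on a different scale from the individual Fpo values reported with them.

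There is a possible knock-on effect. Section 16.3.1 computes the fraction absorbed as Ftot/Fh, where Ftot "is the average total bio-availability estimated in Part 1 of the study". It does not say which estimate is meant. If the ANOVA value were used, the fraction absorbed would carry the same error.

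**Working it through.** The SAP gives no numerical value for the Part 1 ratio, so there is no stated figure to reproduce.

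**Inputs from the SAP**
- D_oral = 800 mg (6.0)
- D_iv = 100 µg = 0.1 mg (5.1, 6.0)
- Fpo = (AUC_oral × D_iv)/(AUC_iv × D_oral) (16.1)
- Model ratio R = exp(LSMean of ln AUC_oral − LSMean of ln AUC_iv) (16.3.2)
- 8 subjects enrolled, at least 6 evaluable (6.1)

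**Step 1: what the model estimates.** Rearranging the 16.1 formula gives AUC_oral/AUC_iv = F × D_oral/D_iv. With complete oral/iv pairs, the LSMean difference equals the mean within-subject log difference. R is therefore the geometric mean of F multiplied by D_oral/D_iv.

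**Step 2: the factor.** D_oral/D_iv = 800/0.1 = 8000, so R = 8000 × F:
- F = 0.05 gives 400
- F = 0.30 gives 2400
- F = 1 gives 8000

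**Step 3: effect on the interval.** The 90% limits for F are F ×/÷ exp(t(0.95, n−1) × √ln(1+CV²) × √(2/n)). F = 0.30 and the two within-subject CVs are assumptions, because the SAP gives no Part 1 value for either.

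| n | CV | 90% CI for F | 90% CI as written (estimate 2400) |
|---|---|---|---|
| 8 | 20% | 0.249–0.362 | 1989–2895 |
| 8 | 60% | 0.177–0.507 | 1419–4058 |
| 6 | 20% | 0.238–0.378 | 1906–3022 |
| 6 | 60% | 0.157–0.572 | 1259–4575 |

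In each row the limits as written are 8000 times those for F, apart from rounding. The upper-to-lower ratio is unchanged.

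**Step 4: sensitivity of the factor.** The SAP fixes neither the concentration units nor the choice of nominal or actual dose.
- If oral AUC were in ng·h/mL and iv AUC in pg·h/mL (assumed), the factor would be 8000/1000 = 8.
- If the actual iv dose were 80 to 120 µg (assumed range), it would be 800/0.08 = 10000 down to 800/0.12 = 6667.

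**Step 5: does the correction recover Fpo?** The check used 200 simulated data sets of 8 subjects, fitted by REML with a random subject effect. The assumed log SDs were 0.35 between subjects, 0.20 residual iv and 0.30 residual oral. With complete pairs, R × D_iv/D_oral divided by the geometric mean of individual Fpo was 1.000 in every run. With one oral AUC missing, the 95% range of that quotient was 0.94–1.06; with two missing it was 0.90–1.08.

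**The case against.** The strongest reply is that the intent is not in doubt. Section 16.1 defines Fpo with both doses, 16.3.2 calls its ratio by the same name, and an absolute bioavailability of 2400 is impossible. The individual values, the interim package (Table 15.2.2 alongside 15.2.3) and the QC of all outputs would very probably expose it. The error is a known constant and loses no data or precision. Section 16.3.1 also speaks of an average clearance, so Ftot reads most naturally as an average of individual, dose-corrected values. That work is assigned to a separate group (3.0).

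Much of this stands. An uncorrected factor of 8000 is unlikely to reach a final report, and the effect on the fraction absorbed is only a possibility. The contradiction remains, however, and a plan should not rely on its primary result looking absurd before someone corrects it. The safeguard also weakens with the units. With the factor of 8 from mixed ng and pg units, an assumed F of 0.05 would be reported as 8 × 0.05 = 0.40, which looks like a bioavailability.

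An unwritten repair also leaves choices open. If actual doses vary between subjects, dividing each AUC by its own dose is not the same as rescaling the final ratio, and it changes the variance. The LSMeans that 16.3.2 also presents would be per unit dose under one repair and raw under the other.

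**Conclusion.** The concern holds. As written, the 16.3.2 rule for Part 1 does not estimate Fpo as 16.1 defines it; it estimates Fpo × D_oral/D_iv. The error is a factor of 8000 in the point estimate and in both 90% limits, given nominal doses and a common concentration unit. Other units or actual doses change the factor, but nothing in the SAP makes it 1. With one nominal dose pair for all subjects, the relative width of the interval is unaffected and the error can be reversed exactly. It must be fixed because it mis-specifies the Part 1 primary estimate and the only stated source of its interval, although no information would be lost.

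**What to change.** In 16.3.2, Part 1, state that the ANOVA is run on ln(AUC0-inf/dose) for oral OZ439 and iv [14C]-OZ439, in common units, with the same D_oral and D_iv as in the 16.1 formula. State also whether those doses are nominal or actual. If a single nominal dose pair applies to all subjects, it is equivalent for the ratio and its interval to multiply the ratio and both limits by D_iv/D_oral = 0.1/800 = 1/8000.

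In 16.3.1, say which Part 1 estimate serves as Ftot.

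Add a QC check that the model result equals the geometric mean of the individual Fpo values. This must hold when every analysed subject has both AUCs, as in the set of 10.4, whose Part 1 members are "considered evaluable for the primary statistical analysis (bioavailability) if they have sufficient PK data to estimate the primary endpoint" Fpo. It need not hold on the PK set of 10.3, which requires reliable estimates of only "at least one of the primary endpoints PK parameters or secondary endpoint parameters".

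The cost of the main change is one sentence in the SAP and one line of code, with no new data.

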### Part 2:

An analysis of variance (ANOVA) will be performed on OZ439 PK parameters  $C_{max}$ ,  $C_{168h}$ ,  $AUC_{0-168}$  and  $AUC_{0-\infty}$  using the SAS procedure for mixed effect models (PROC MIXED). The PK parameters will be natural logarithm transformed prior to analysis. The model will include fixed effects for treatment, period, and sequence, and a random effect for subject within sequence (comparisons D vs C and B vs C; for comparison B vs A only a fixed effect for treatment will be included).

From the ANOVA model the back-transformed least-squares means (LSMeans) for test and reference treatments will be presented. The ratios of the LSMean for the comparison of the treatments D vs C, B vs A and B vs C will be obtained by exponentiating the difference of the LSMean on the log scale. This ratio and the corresponding 90% CI will be presented for the comparisons between:

- Treatment D vs Treatment C to assess the effect of cobicistat on OZ439
- Treatment B vs Treatment A to explore volume effect (for this no within-subject comparison is possible)
- Treatment B vs Treatment C to explore dosing solution concentration effect (Treatment C will be dose normalized to 800 mg (only for this comparison))

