#### 5.2 Secondary

- To assess the safety and tolerability of OZ439 when administered alone, and to assess the safety and tolerability of OZ439 and cobicistat when co-administered as single doses to healthy subjects (Parts 1 and 2)
- To determine the PK parameters of OZ439 single iv microdose (100 µg) infusion of [C]-OZ439 (Part 1)

- To assess the effects of the total dosing volume and of dose to volume ratio on OZ439 PK under fasted conditions (Parts 1 and 2)
- To determine the PK parameters and exposures of cobicistat (Part 2)

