### 9.4.2 Predetermined Covariates and Prognostic Factors

There are no predetermined covariates or prognostic factors.

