## 16.2 Pharmacokinetic Concentrations

Plasma concentrations for total radioactivity, [C]-OZ439, OZ439 or cobicistat below the quantifiable limit (BQL) will be set to ½ LLOQ in the computation of mean concentration values. Descriptive statistics (number of subjects, arithmetic mean, geometric mean, SD, CV%, median, minimum, and maximum) will be used to summarize the plasma concentrations by treatment at each scheduled time point. If over ½ the subjects in a given cell have values BQL then the descriptive statistics will not be presented except for the minimum and maximum and the mean will be displayed as BQL.

Linear and semi-logarithmic plots of the geometric mean total radioactivity, OZ439 and cobicistat plasma concentration by scheduled sampling time will be provided by treatment. These plots will show time in hours. The plots will match the summary table results and will not have an observation at a given time point if more than half of the subjects have values BQL. The following mean plots will be provided:

- Geometric mean oral OZ439 concentration, iv total radioactivity and OZ439 specific radioactivity versus time plot (in the same plot). A linear plot including SD bars, and a semi-logarithmic plot will be provided [treatment A, Part 1].
- Geometric mean oral OZ439 concentration vs time plot for treatments C and D in the same plot. A linear plot including SD bars, and a semi-logarithmic plot will be provided [Part 2].
- Geometric mean oral OZ439 concentration vs time plot for treatments A, B and C (with C dose-normalized to 800mg) in the same plot. A linear plot including SD bars, and a semi-logarithmic plot will be provided [Part 1 and 2].
- Mean plot of oral cobicistat concentration vs time (linear) [treatment D, Part 2].

Linear and semi-logarithmic plots of the combined individual plasma concentration by actual sampling time will be provided in a single plot by treatment and analyte (total radioactivity, OZ439, [C]-OZ439 and cobicistat).

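### Do the volume and concentration labels on B vs A and B vs C conflict, so that a contrast for volume at equal concentration must be added?

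*SAP*

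**What the plan says.** Section 6.0 of the SAP defines the three oral treatments without cobicistat. A is "a single oral dose of 800 mg OZ439 simple granules administered as a 100-mL dispersion", B is the same dose in 64.5 mL, and C is "a single oral dose of 400 mg OZ439 simple granules administered as a 64.5-mL dispersion". A is given in Part 1 (8 subjects). B and C are given in the Part 2 crossover (18 subjects).

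A secondary objective in Section 5.2 is "To assess the effects of the total dosing volume and of dose to volume ratio on OZ439 PK under fasted conditions". A primary objective in Section 5.1 concerns PK when the target dosing volume is restricted to 64.5 or 100 mL.

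Section 16.3.2 serves these objectives with two ratios and 90% CIs: "Treatment B vs Treatment A to explore volume effect" and "Treatment B vs Treatment C to explore dosing solution concentration effect". C is dose-normalised to 800 mg for the second. On the model, it says that "for comparison B vs A only a fixed effect for treatment will be included", and it notes that B vs A cannot be made within subjects. Section 16.2 adds a descriptive figure: "Geometric mean oral OZ439 concentration vs time plot for treatments A, B and C (with C dose-normalized to 800mg) in the same plot".

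**The concern.** The objective names two effects and Section 16.3.2 gives each its own contrast, so a reader may take the contrasts as separating them. They do not. A, B and C have three different concentrations, so no pair differs in volume at equal concentration. B vs A changes both at once.

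If the dose-normalised B/C ratio really is a concentration effect, part of it reappears in B/A. A pure concentration effect could then be reported as a volume effect, or a real volume effect could be cancelled by an opposite concentration effect. Section 9.4.2 states "There are no predetermined covariates or prognostic factors", and no planned model combines A, B and C. The B vs C label also rests on dose proportionality from 400 to 800 mg, which the SAP does not state.

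The apparent remedy is an added ratio: interpolate B and normalised C to A's concentration within each Part 2 subject, then compare the result with A.

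**Working it through.** The SAP gives no figure for these two contrasts, so there is none to reproduce. Below, Cn is C normalised to 800 mg.

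**Concentrations (Section 6.0)**
- A: 800/100 = 8.00 mg/mL
- B: 800/64.5 = 12.40 mg/mL
- C: 400/64.5 = 6.20 mg/mL

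**Share of the concentration step in B vs A**
- B vs A: ln(12.40/8.00) = 0.4385, a 1.55-fold step
- B vs C: ln(12.40/6.20) = 0.6931, a 2-fold step
- Share on log concentration: 0.4385/0.6931 = 0.633
- Share on linear concentration: (12.40 − 8.00)/(12.40 − 6.20) = 0.71

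**If B/Cn is wholly a concentration effect.** With no volume effect, B/A = (B/Cn)^0.633:
- 0.80 gives 0.87
- 0.90 gives 0.94
- 1.10 gives 1.06
- 1.25 gives 1.15

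A true volume ratio of 1.15 combined with B/Cn = 0.80 gives B/A = 1.15 × 0.868 = 1.00.

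**The candidate added contrast.** Its estimate is 0.367 ln B + 0.633 ln Cn − ln A, which equals ln(B/A) − 0.633 ln(B/Cn). At 8.0 mg/mL, 64.5 mL holds 8.0 × 64.5 = 516 mg. The contrast therefore sets a notional 516 mg dose against A's 800 mg: it removes a concentration difference by bringing in a dose difference.

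**If B/Cn is wholly dose non-proportionality.** With exposure proportional to dose^p, B/Cn = 2^(p−1). B/Cn = 0.80 then needs p = 1 + ln 0.80/ln 2 = 0.68. A and B are both 800 mg, so B/A = 1.00. The added contrast reads 0.80^(−0.633) = 1.15 with no volume effect present.

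**How often a 90% CI excludes 1 when volume has no effect.** Simulation of 40,000 trials, 18 vs 8 subjects, B/Cn = 0.80. The within-subject CV is 23% (the figure Section 6.1 gives for the cobicistat comparison). The total CV of 30% or 60% is an assumption. Ranges cover pooled and unequal-variance (Welch) analyses.

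| Cause of B/Cn = 0.80 | Contrast | Total CV 30% | Total CV 60% |
|---|---|---|---|
| Concentration | B vs A | about 29% | about 15% to 16% |
| Concentration | Added | 10% (Welch), 12% (pooled) | about 10% |
| Dose non-proportionality | B vs A | about 10% | about 10% |
| Dose non-proportionality | Added | 30% (Welch), 35% (pooled) | about 16% |

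**Precision.** With total variance ln(1 + CV²):
- The SE of ln(B/A) is 0.1247 at CV 30% and 0.2356 at CV 60%. With t(0.95, 24 df) = 1.711, the 90% CI factors are exp(1.711 × 0.1247) = 1.24 and exp(1.711 × 0.2356) = 1.50.
- The added contrast has factors 1.23 and 1.49, so it neither gains nor loses precision.
- The largest illustrative shifts above, 0.87 and 1.15, lie inside the B/A factor even at CV 30%.

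**The case for a change.** The strongest case for a change is that the objective distinguishes total volume from dose-to-volume ratio while the estimators do not. The SAP nowhere says that B and A differ in concentration. The B vs C label already depends on proportionality, so a further ratio on the same assumption asks for nothing new. It would cost one table line per parameter and no precision.

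Much of this stands. The arithmetic is right, B vs A is not volume at fixed concentration, and the proportionality assumption is unstated.

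The step from there to a better analysis does not stand. Three oral cells give two contrasts, and there are three unknowns: volume, concentration and departure from dose proportionality. The added ratio identifies volume only by setting the third to zero. B vs A needs no such assumption, because A and B share a dose. Sharing the assumption with B vs C is no advantage: it would carry the weakness of B vs C into the volume comparison, which is now free of it. The weights depend on an interpolation scale (0.633 or 0.71) that the SAP does not give. The new ratio would also inherit the non-randomised comparison across study parts, with the iv microdose in A only.

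**Conclusion.** No change to the plan is needed. B vs A answers a well-defined question: what happens to exposure when 800 mg is given in 64.5 rather than 100 mL. That matches the volume restriction in Section 5.1, and at a fixed dose the 1.55-fold change in concentration is part of the effect. The labels conflict only if volume effect is read as volume at equal concentration, which the SAP does not say.

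The interpolated contrast is a trade-off, not a gain. For B/Cn = 0.80 it protects against a false volume signal of about 29% (CV 30%) or 15% (CV 60%) when the cause is concentration. It creates one of about 30% to 35% or 16% when the cause is dose non-proportionality. The document does not say which cause is more likely. These rates rest on the assumed CVs and on log-linear interpolation.

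Little is withheld from the reader. Both B/A and B/Cn are to be reported with CIs, so the combined point estimate follows from them by the formula above, up to small model differences; only its interval is missing. The study is called exploratory in Section 6.1, these comparisons have no decision rule, and D vs C and absolute bioavailability are untouched. Describing B vs A as a fixed-dose comparison, and noting that B vs C assumes proportionality, is ordinary care in interpreting the results and can be left to the report.
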